8.2.1.2 Overall survival (secondary endpoint)

Overall survival is counted from the date of registration. Patients who die are reported as events, irrespective of the cause of death. Patients without the event of interest are censored at the time of most recent follow-up visit.

8.2.1.3 Adverse events (secondary endpoint)

Side effects of the treatment will be assessed using the NCI-CTCAE version 3.0. The analysis will focus on the worst grade of acute adverse events reported by the patients, as well as the worst grade of late adverse events (i.e. reported on follow-up forms to have occurred 3 months or more after the end of irradiation).

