2.2 End-points

The primary trial endpoint is progression-free survival where progression is defined on the basis of tumor growth or appearance of new lesions (see chapter 7 for exact definition).

The secondary trial endpoints are acute and late effects classified according to the National Cancer Institute Common Terminology Criteria for Adverse Events v 3.0 (NCI CTCAE v3.0), mini-mental status (MMSE) and overall survival.

Quality of life is not an endpoint in this study since the trial is not randomized and is of relatively small size.

3 Patient selection criteria

Patients will be registered between surgery and the start of radiotherapy without exceeding 6 weeks time interval.

- ◆ **Histologically proven newly diagnosed atypical grade WHO grade II meningioma** (≥ 4 mitosis per high-power field [HPF] or the presence of at least 3 of the latter 4 variables: cellularity, architectural sheeting (i.e. patternless pattern), macronuclei and small cell formation) (see section 3.2 below for definition)

OR

- ◆ **Histologically proven newly diagnosed malignant WHO grade-III meningioma** (see section 3.2 below for definition)

(as assessed by the local pathologist)

AND all of:

- ◆ Complete or subtotal resection as assessed by the surgeon after verification with a postoperative MRI and according to Simpson guidelines (see section 3.4 below for definition). The patients will be stratified according to the resection status: complete excision (Simpson's stages 1-3) versus incomplete excision (Simpson's stages 4-5)
- ◆ Age between 18 years and 70 years
- ◆ WHO performance status 0-2
- ◆ All locations except optic nerve sheath tumors
- ◆ No neurofibromatosis type II patients (NF-2)
- ◆ No previous radiotherapy to the brain or meninges interfering with the protocol treatment plan
- ◆ No clinical evidence of second malignancies, except a history of cervix carcinoma in situ and basocellular carcinoma
- ◆ Women of reproductive potential must use effective contraception for the whole duration of the treatment and must not be pregnant or lactating.
- ◆ Absence of any psychological, familial, sociological or geographical condition potentially hampering compliance with the study protocol and follow-up schedule; those conditions should be discussed with the patient before registration in the trial
- ◆ Before patient registration, written informed consent must be given according to ICH/GCP, and national/local regulations.

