6.1 Before treatment start

The following evaluations have to be done:

- ◆ Local histology certifying meningioma WHO grade II or III. Mitotic index and if possible, MIB-1 index and, in women the progesterone/estrogen receptor status.
- ◆ Contrast enhanced pre and post-operative MRI in at least 2 plans. The post-operative MRI brain study should be done within 48 hours of the operation.

- ◆ Complete medical history including medications
- ◆ Physical examination including the performance scale evaluation (WHO performance scales see Appendix B)
- ◆ Mini-Mental Status Examination (MMSE, see Appendix F)

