6.4 Summary table

	Baseline prior to entry	At 6 weeks after the last day of irradiation	Follow-up at 6 months after entry	Follow-up at month 12 and then yearly
Histological diagnosis	X			
MRI brain study (Gd+)	X	NO	X	△
Medical history	X	X	X	△
Physical examination	X	X	*	*
Performance Status	X	X	X	△
Concomitant medication	X	X	X	△
Mini-mental status	X	X	X	△
Adverse events scoring (CTCAE v.3.0)	X (acute)	X (acute)	X (late)	△ (late)
Survival		X	X	X

X Mandatory

* Recommended

△ Until tumor progression

7 Criteria of evaluation

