8.2.3.3 Analysis methods for safety endpoints

The frequency of the worst grade of acute adverse events reported by the patients will be tabulated in each of the four patient groups described in section 8.1.2.

The worst grade of late adverse events (i.e. reported on follow-up forms to have occurred 3 months or more after the end of irradiation) will also be tabulated. The time to the occurrence of any severe late adverse events will be estimated by Kaplan-Meier method, with the time counted from entry on study to the first reported late adverse events grade 3 or 4 and with censoring at the time of last examination of the patients who did not report any such event. The rate of late severe adverse events will be estimated similarly by means of cumulative incidence curves (Ref. 107) with 2-sided 95% confidence intervals at specified time points.

No formal statistical tests will be performed.

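### The worst-grade toxicity analysis makes no use of the pre-treatment CTCAE score, so pre-existing deficits may be counted as radiotherapy toxicity

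*Protocol*

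**What the plan says.** Section 8.2.1.3 states "Side effects of the treatment will be assessed using the NCI-CTCAE version 3.0" and defines the summary: "The analysis will focus on the worst grade of acute adverse events reported by the patients, as well as the worst grade of late" toxicity. Late events are those "reported on follow-up forms to have occurred 3 months or more after the end of irradiation". Acute events are given no time window.

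Section 8.2.3.3 sets the tables: "The frequency of the worst grade of acute adverse events reported by the patients will be tabulated in each of the four patient groups". It also estimates the time to severe late toxicity, "with the time counted from entry on study to the first reported late adverse events grade 3 or 4". Neither section mentions a baseline grade, new onset, worsening or causality.

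The schedule in 6.4 has a row "Adverse events scoring (CTCAE v.3.0") that is mandatory in the column before entry. The entry there is marked acute, the same mark as the score six weeks after the last irradiation. The text list in 6.1 names items such as "Complete medical history including medications", physical examination and MMSE, but no CTCAE scoring.

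On timing, chapter 3 opens with: "Patients will be registered between surgery and the start of radiotherapy without exceeding 6 weeks time interval".

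**The concern.** Patients enter shortly after intracranial surgery, and section 1.2 says that non-benign tumors seldom come without symptoms. Some patients can therefore be expected to start radiotherapy with a neurological or visual deficit. A worst-grade rule without a baseline comparison has no means of separating such a deficit from an effect of irradiation. It also cannot separate a worsening to grade 3 from a grade 3 that has not changed.

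Treatment tolerance is one of the trial's objectives, and section 2.1 makes acceptable toxicity one of the conditions for considering a phase III trial. There is no control group to show the background rate. The groups are small: at the planned sizes, one misattributed patient adds 1/25 = 4.0 percentage points in the Simpson 1-3 group and 1/39 = 2.6 points in the Simpson 4-5 group.

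**Working it through.** The protocol states no toxicity rate, so there is no figure to reproduce. Its sample sizes concern progression-free survival only and are not affected.

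**Step 1: can a pre-irradiation grade enter the acute table?** Section 8.2.1.3 bounds late events in time but gives acute events no start. The table in 6.4 marks the pre-entry score as acute. Read literally, that score is one of those from which the worst acute grade is taken. This needs no assumption about prevalence.

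**Step 2: can a persisting deficit enter the late table?** The first visit with late scoring is 6 months (about 26 weeks) after entry. Radiotherapy starts at most 6 weeks after entry and lasts 6 or 7 weeks. Without interruptions, that visit falls at least 26 - 6 - 7 = 13 weeks after the end of irradiation (14 weeks for the 6-week course), which is about 3 months. A deficit still scored at that visit falls inside the late window if the rule is read as presence or first report. It falls outside if the rule is read as onset. Section 8.2.1.3 speaks of events that occurred, while 8.2.3.3 times the first one reported. The text does not settle which reading applies.

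**Step 3: is there another filter?** Section 14.2.2 excludes unworsened pre-existing conditions, but only from SAE reporting. It also requires a causality assessment, which 8.2.1.3 and 8.2.3.3 do not use. By contrast, 8.2.3.4 analyses MMSE as change, with a 3-point threshold.

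**Step 4: how large could the effect be?** The documents give neither of these inputs, so both are assumed:
- b = share of patients with a persistent grade 3 or higher deficit at entry, 0-20%
- t = true rate of new grade 3 or higher events, 5% or 10%

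If b and t are independent and every such deficit is recorded again as an adverse event, the apparent rate is 1 - (1 - b)(1 - t).

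| b | t = 5% | t = 10% |
|---|---|---|
| 0% | 5.0% | 10.0% |
| 5% | 9.8% | 14.5% |
| 10% | 14.5% | 19.0% |
| 20% | 24.0% | 28.0% |

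For example, with b = 10% and t = 5%: 1 - 0.90 × 0.95 = 0.145. Among 64 patients that is 64 × 0.145 = 9.3 counted, against 64 × 0.05 = 3.2 with a new event. The share counted only for a pre-existing deficit is 0.10 × 0.95 / 0.145 = 66%.

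The formula applies to either table. Each entry is an upper bound for its b and t, because full re-recording is assumed.

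**The case against.** The case on the other side has several parts.

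- **Late events.** The definition can be read as requiring onset after irradiation, which would exclude a deficit present at entry. This stands as a partial shield. A reader might infer that every persistent grade 3 deficit becomes a late grade 3 event; the wording does not support that.
- **What is scored.** The protocol speaks of side effects of treatment and requires a causality judgement, and nothing tells sites to score a stable surgical deficit again. A reader might infer that such deficits will be reported as radiotherapy toxicity. The documents support only that they may be, since neither provision is carried into the tables.
- **Prevalence.** The remark in 1.2 describes tumors at presentation, not severe deficits after surgery, and entry requires WHO performance status 0-2. This stands: the range used for b is assumed, and at b = 0 there is no bias.
- **Masking.** A reader might infer that worst grade hides worsening in patients who start at grade 1 or 2. It does not hide a rise to grade 3, which both the worst grade and the time-to-event analysis capture.
- **Background rate.** Section 8.2.6 tabulates all categorical CRF variables, so the baseline distribution would be visible if it is collected. That is a separate margin and does not show who changed.
- **Level of detail.** Baseline rules are often left to a separate SAP, and the safety analysis is descriptive with no toxicity threshold. However, section 8.2 is itself headed as the statistical analysis plan and states the rule, and the acute label in 6.4 is a fault in the protocol itself.

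**Conclusion.** The point holds in a limited form. As written, the analysis does not use the pre-treatment CTCAE score, and the label in 6.4 allows that score to enter the worst acute grade. Pre-existing deficits may therefore be counted as toxicity, most clearly in the acute table and less certainly in the late one.

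The size is unknown. Under the stated assumptions (0-20% with a persistent severe deficit, always recorded again, independent of new events), a true 5% would appear as 5% to at most 24%, and a true 10% as 10% to at most 28%. These are bounds on an illustration and not predictions for this trial.

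It is also not secure that the baseline score is collected, since 6.4 requires it and 6.1 omits it. The primary endpoint is untouched.

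**What to change.** 1. In 6.4, relabel the pre-entry CTCAE entry as baseline, and state in 8.2.1.3 that it does not count toward the worst acute grade.
2. Reconcile 6.1 with 6.4 so that baseline CTCAE scoring is listed in both.
3. In 8.2.1.3 and 8.2.3.3, tabulate worst grade by baseline grade, and count an event only if it is new or of higher grade than the same item at baseline.
4. Define the severe-late-event time by the first late grade 3 or 4 event that is a worsening over baseline.

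The cost is small: analysis programming, and making sure the baseline CTCAE form is completed. Patient numbers and the progression-free survival design do not change.

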8.2.1.4 Mini Mental-State Examination (MMSE, secondary endpoint)

The Mini Mental State Examination (MMSE) is a brief, standardized tool to grade patients' cognitive function. It is an 11-question measure that tests five areas of cognitive function: orientation, registration, attention and calculation, recall, and language. The maximum score is 30.

Since its creation in 1975 by Folstein et al (Ref. 102), the MMSE has been validated and extensively used in both clinical practice and research.

Following Tangalos et al. (Ref. 103) and as previously used by Brown et al (Ref. 104) a decline of more than 3 points in the MMSE score will be considered to represent clinically significant deterioration.

Following Brown et al, the patient's cognitive function will be considered 'impaired' if the MMSE score is 26 or less and 'normal' if it is 27 or more.

The evolution of the MMSE evaluation over time will be interpreted in the light of attrition induced by the fact that patients are assessed only until progression. All MMSE results will thus be conditional on the patients being otherwise free of progression.

8.2.2 Analysis populations

- ◆ Intention-to-treat population: all patients entered in the study
- ◆ Per protocol population: all patients who are eligible and have started the planned treatment (at least one fraction of irradiation)
- ◆ Safety population: all patients who have started the planned treatment (at least one fraction of irradiation)

A patient will be considered to be eligible if he/she did not have any major deviations from the patient entry criteria listed in chapter 3 of the protocol. Eligibility will be assessed by the Study Coordinator based on the review of each patient file.

For eligibility and stratification (WHO II vs WHO III), the histology assessed by the local pathologist will be considered.

8.2.3 Statistical methods

8.2.3.1 Primary analysis population

The primary analysis of the efficacy endpoints (progression-free survival and overall survival) will be performed in the per protocol population.

The primary analysis of the safety endpoints (acute and late adverse events) will be performed in the safety population.

Each analysis will be performed separately in the four groups defined in section 8.1.2, but for the efficacy endpoints and the grade III meningiomas in whom, due to small numbers, the analysis will be carried out in the pooled group of grade III meningiomas, irrespective of Simpson's stage.

8.2.3.2 Analysis methods for activity endpoints

The primary endpoint, progression-free survival rate at 3 years, will be estimated by the Kaplan-Meier technique (Ref. 105). The variance will be estimated by the Greenwood formula (Ref. 106). The one-sided lower 90% confidence interval will be calculated using Log-Log transform to assess the primary protocol conditions for success. The same method will be used for estimating the 2-sided 95% confidence intervals.

The secondary endpoint overall survival will be analyzed by the same methods as the primary endpoint, but the 1-sided 90% confidence interval will not be displayed (the confidence intervals will be 2-sided at 95%).

8.2.3.3 Analysis methods for safety endpoints

The frequency of the worst grade of acute adverse events reported by the patients will be tabulated in each of the four patient groups described in section 8.1.2.

The worst grade of late adverse events (i.e. reported on follow-up forms to have occurred 3 months or more after the end of irradiation) will also be tabulated. The time to the occurrence of any severe late adverse events will be estimated by Kaplan-Meier method, with the time counted from entry on study to the first reported late adverse events grade 3 or 4 and with censoring at the time of last examination of the patients who did not report any such event. The rate of late severe adverse events will be estimated similarly by means of cumulative incidence curves (Ref. 107) with 2-sided 95% confidence intervals at specified time points.

No formal statistical tests will be performed.

8.2.3.4 Analysis methods for the Mini mental-state examination (MMSE)

The proportion of patients with 'normal' and 'impaired' MMSE score at baseline and at key time-points of evaluation (eg. Baseline, year 1, year 2 etc..) will be displayed in the four patient groups defined in section 8.1.2.

Similarly to Brown et al. (Ref. 104) the changes in MMSE scores over time will be summarized in the two treatment groups by the proportion of patients with significant increase (>+3 points), stable (-3 points to +3 points) or significant decrease (decrease of >3 points) of the MMSE score at the key time points of evaluation.

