2.1 General objectives

The objectives of this study are to assess the impact of high-dose radiotherapy (RT) on progression-free survival (PFS), treatment tolerance, and post-treatment global cognitive functioning in patients with a diagnosis of either atypical (grade WHO II) or malignant (grade WHO III) meningioma.

The atypical meningioma patients will be entered in one of two strata of a non-randomized phase II study, depending on the Simpson's stage achieved by surgery. The malignant meningioma patients will be registered in a separate stratum. For the latter group, no strict statistical design is planned due to the expected small patient number.

This study is the first one assessing the value of post-operative high-dose radiotherapy in grade II and grade III meningioma patients and the results will serve as a basis for designing future studies in this disease. If the patient accrual rate is high enough and if dose escalation to 60 or 70 Gy demonstrates sufficient activity with acceptable toxicity, a phase III trial might be considered in the future.

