6.3.2 The further follow-up

The next follow-up will be at 6 months after entry on study, then at month 12 and then annually.

Until disease progression, every scheduled follow-up visit includes the following evaluation (see table in chapter 6.4).:

- ◆ Clinical examination, performance status evaluation (WHO-ECOG), interim medical history.
- ◆ Concomitant medications
- ◆ Mini-Mental Status Examination (MMSE, see Appendix F)
- ◆ Late adverse events scoring according to the National Cancer Institute Common Terminology Criteria for Adverse Events (CTCAE) v.3.0 (<http://ctep.cancer.gov/forms/CTCAEv3.pdf>) grading system.
- ◆ Contrast enhanced (gadolinium) MRI (T1, T1 Gado, T2) with slice thickness of 3-5 mm.

After disease progression, the patients will only be followed-up for survival.

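### The normal/impaired MMSE table compares a baseline column not restricted to later-assessed patients with later columns of progression-free patients only, so the impaired share can fall without any patient improving

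*Protocol*

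**What the plan says.** Section 2.1 of the protocol lists among its objectives the effect of high-dose radiotherapy on "post-treatment global cognitive functioning in patients with a diagnosis of either atypical (grade WHO II) or malignant (grade WHO III) meningioma". It does not restrict this to patients who remain progression-free.

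The MMSE is a secondary endpoint. Under section 6.3.2 it is done at scheduled visits only while the patient has not progressed ("Until disease progression, every scheduled follow-up visit includes the following evaluation"); after that, "After disease progression, the patients will only be followed-up for survival". The table in section 6.4 agrees from month 12 onward. It marks the 6-month MMSE as mandatory without that limit, but the yearly time points at issue here are not affected.

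Section 8.2.3.4 plans two summaries:

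- by the four grade-by-resection groups, "The proportion of patients with 'normal' and 'impaired' MMSE score at baseline and at key time-points of evaluation", with baseline, year 1 and year 2 given as examples;
- individual change: "the changes in MMSE scores over time will be summarized in the two treatment groups by the proportion of patients with significant increase", stability or significant decrease, with a threshold of more than 3 points.

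Section 8.2.1.4 sets the cut-off (26 or less is impaired) and adds two caveats. The course of the MMSE "will be interpreted in the light of attrition induced by the fact that patients are assessed only until progression", and "All MMSE results will thus be conditional on the patients being otherwise free of progression".

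Section 8.2.3.1 names analysis populations for the efficacy and safety endpoints but none for the MMSE.

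**The concern.** A reader of the first summary will look along the row from baseline to year 1, year 2 and year 3 and take the difference as cognitive change. With the display as written, that difference has two components: change within patients, and change in which patients are counted. The second component is not noise if baseline cognition is related to progression or death. If impaired patients leave sooner, the later columns are depleted of them and cognition seems to improve. If they leave later, the display errs in the other direction.

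The loss is not small on the protocol's own planning rates. By year 3, 30% to 50% of the Simpson 4-5 stratum and 10% to 30% of the Simpson 1-3 stratum would have left the MMSE set. What is at stake is the reading of a stated objective of the trial, not its primary endpoint or any decision rule.

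**Working it through.** **Inputs from the protocol.** Section 8.1.1: 25 patients (Simpson 1-3) and 39 (Simpson 4-5). Sections 8.1.1.1 and 8.1.1.2: 3-year PFS of 70% (P0) or 90% (P1), and 50% (P0) or 70% (P1), respectively. The protocol states no expected MMSE figure that could be reproduced. The designs that supply these rates do reproduce with exact binomial rules: 25 patients with success at 21 or more gives α = 0.0905 and β = 0.0980 (stated 0.09 and 0.098); 39 patients with success at 24 or more gives α = 0.0998 and β = 0.0944 (stated 0.10 and 0.094).

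**Patients still assessable at year 3**, if every progression-free patient attends: 25 × 0.7 = 17.5 to 25 × 0.9 = 22.5, and 39 × 0.5 = 19.5 to 39 × 0.7 = 27.3.

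**Assumptions, not in the protocol.** Baseline impaired share π = 30%; hazard ratio h for progression or death, impaired versus normal, from 1 to 3; no patient's MMSE category ever changes; every patient has a baseline MMSE.

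**Model.** Let S be the overall 3-year PFS and s the 3-year PFS of normal patients, so that impaired patients have s^h. Solve

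(1 − π)·s + π·s^h = S

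and the impaired share among those still progression-free is π·s^h / S.

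For h = 2:

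- S = 0.5: 0.7s + 0.3s² = 0.5 gives s = 0.573 and s² = 0.329; share = 0.3 × 0.329 / 0.5 = 19.7%.
- S = 0.7: s = 0.755 and s² = 0.571; share = 0.3 × 0.571 / 0.7 = 24.5%.
- S = 0.9: s = 0.922 and s² = 0.849; share = 0.3 × 0.849 / 0.9 = 28.3%.

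| 3-year PFS | h = 1 | h = 1.5 | h = 2 | h = 3 |
|---|---|---|---|---|
| 50% | 30.0% | 24.0% | 19.7% | 13.9% |
| 70% | 30.0% | 26.8% | 24.5% | 21.1% |
| 90% | 30.0% | 29.0% | 28.3% | 27.3% |

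Against 30% at baseline, the apparent improvement at h = 2 is 10.3, 5.5 and 1.7 points.

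**Sensitivity to the form of the assumption.** Suppose instead that impaired patients have twice the 3-year *risk* of progression or death. The risk in normal patients is then f = (1 − S)/(2π + 1 − π) and the later share is π(1 − 2f)/S. With π = 30% this gives 13.8% at S = 50%, 23.1% at S = 70% and 28.2% at S = 90%, that is, falls of 16.2, 6.9 and 1.8 points. The hazard-ratio figures are the more cautious of the two.

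**Effect of a matched baseline.** If each later column is set beside the baseline share of the same patients, the two are equal whenever no one changes, so the artefact is zero by construction for any π, h and S.

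**The case against.** The strongest reply is that the protocol already says this. Section 8.2.1.4 declares every MMSE result conditional on freedom from progression, which amounts to choosing cognition while progression-free as the target. That is a defensible choice: section 5.5 leaves therapy after progression to the treating physician, so later scores would mix the effect of radiotherapy with relapse and further treatment. The individual-change summary in section 8.2.3.4 compares each patient with his or her own baseline, and clinically significant deterioration is defined on that change. The baseline denominator is not stated, so it is an inference that it contains everyone. The size rests on two assumed quantities. At the P1 rates the illustrated artefact (5.5 and 1.7 points) is below the standard error of such a share: with 24.5% in 27.3 patients, √(0.245 × 0.755 / 27.3) is about 8 points.

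Much of this stands. It limits the point to one of two displays and makes the numbers illustrative. It does not remove the point. A caveat about interpretation leaves the table as it is, and a baseline column of all patients would not meet the condition that section 8.2.1.4 sets for all MMSE results. Systematic error also adds to sampling error rather than being excused by it. Nor is this detail left for a later document: section 8.2 is the protocol's own statistical analysis plan and specifies the display, the cut-off and the change categories.

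A reader might go further and infer that the cognitive objective is not answered at all, or that the analysis is biased in favour of high-dose radiotherapy. The documents support neither. The objective is answered for patients while progression-free. The direction of any bias depends on a relation between baseline cognition and progression that the protocol does not give. No decision rule uses the MMSE, and the condition in section 2.1 for considering a phase III trial refers to activity and acceptable toxicity, with toxicity assessed by CTCAE grade.

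**Conclusion.** The point holds in a limited form. The normal/impaired display sets a baseline proportion with no stated restriction beside later proportions that can include only progression-free patients, and the impaired share can fall through selection alone. With 30% impaired at baseline and a hazard ratio of 2, both assumed, the fall by year 3 is about 10 points at 50% PFS, 5.5 at 70% and 1.7 at 90%. The 10-point figure belongs to the rate that the protocol itself regards as too low in the Simpson 4-5 stratum. At a hazard ratio of 1 there is no artefact. The disclosure in section 8.2.1.4 and the paired change summary reduce the risk of misreading but do not correct this table. Both MMSE summaries describe cognition while progression-free, which is narrower than the objective in section 2.1. This is a cheap improvement to a secondary endpoint, not a flaw in the trial's main conclusions.

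**What to change.** In section 8.2.3.4:

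1. At each time point, give the number assessed and the baseline normal/impaired proportion in those same patients, as a paired shift table. This removes the composition artefact.
2. Add one descriptive display with all treated patients who have a baseline MMSE as denominator. Either show, at each year, the shares who have declined by more than 3 points, not declined, progressed, died or have a missing score; or show the cumulative incidence of a first decline of more than 3 points before progression, with progression and death as competing events. Section 8.2.3.3 already plans cumulative incidence curves for severe late adverse events, so the method is at hand.
3. Label the existing MMSE tables as results in progression-free patients.

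While the section is open, reconcile its group definitions: the first summary uses four patient groups and the second refers to two treatment groups.

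The cost is two extra descriptive tables or curves per group, with no new visits, data or patients. Two limits remain. Decline can be dated only to the scheduled visit, mostly yearly, and cognition after progression stays unobserved because it is not collected.
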